12.2.2 Disease Parameters

12.2.2.1 **Measurable disease:** Measurable lesions are defined as those that can be accurately measured in at least one dimension (longest diameter to be recorded) as ≥ 20 mm by chest x-ray, as ≥ 10 mm with CT scan, or ≥ 10 mm with calipers by clinical exam. All tumor measurements must be recorded in millimeters (or decimal fractions of centimeters).

NOTE: Tumor lesions that are situated in a previously irradiated area might or might not be considered measurable. If the investigator thinks it appropriate to include them, the conditions under which such lesions should be considered must be defined in the protocol.

12.2.2.2 **Malignant lymph nodes:** To be considered pathologically enlarged and measurable, a lymph node must be ≥ 15 mm in short axis when assessed by CT scan (CT scan slice thickness no greater than 5 mm). At baseline and in follow-up, only the short axis will be measured and followed.

12.2.2.3 **Non-measurable disease:** All other lesions (or sites of disease), including small lesions (longest diameter < 10 mm or pathological lymph nodes with ≥ 10 to < 15 mm short axis), are considered non-measurable disease. Bone lesions, leptomeningeal disease, ascites, pleural/pericardial effusions, lymphangitis cutis/pulmonitis, inflammatory breast disease, and abdominal masses (not followed by CT or MRI), are considered as non-measurable.

NOTE: Cystic lesions that meet the criteria for radiographically defined simple cysts should not be considered as malignant lesions (neither measurable nor non-measurable) since they are, by definition, simple cysts. 'Cystic lesions' thought to represent cystic metastases can be considered as measurable lesions, if they meet the definition of measurability described above. However, if non-cystic lesions are present in the same patient, these are preferred for selection as target lesions.

12.2.2.4 **Target lesions:** All measurable lesions up to a maximum of 2 lesions per

organ and 5 lesions in total, representative of all involved organs, should be identified as target lesions and recorded and measured at baseline. Target lesions should be selected on the basis of their size (lesions with the longest diameter), be representative of all involved organs, but in addition should be those that lend themselves to reproducible repeated measurements. It may be the case that, on occasion, the largest lesion does not lend itself to reproducible measurement in which circumstance the next largest lesion that can be measured reproducibly should be selected. A sum of the diameters (longest for non-nodal lesions, short axis for nodal lesions) for all target lesions will be calculated and reported as the baseline sum diameters. If lymph nodes are to be included in the sum, then only the short axis is added into the sum. The baseline sum diameters will be used as reference to further characterize any objective tumor regression in the measurable dimension of the disease.

12.2.2.5 **Non-target lesions:** All other lesions (or sites of disease) including any measurable lesions over and above the 5 target lesions should be identified as non-target lesions and should also be recorded at baseline. Measurements of these lesions are not required, but the presence, absence, or in rare cases unequivocal progression of each should be noted throughout follow-up.

12.2.3 **Methods for Evaluation of Measurable Disease**

All measurements should be taken and recorded in metric notation using a ruler or calipers.

The same method of assessment and the same technique should be used to characterize each identified and reported lesion at baseline and during follow-up. Imaging-based evaluation is preferred to evaluation by clinical examination unless the lesion(s) being followed cannot be imaged but are assessable by clinical exam.

12.2.3.1 **Clinical lesions:** Clinical lesions will only be considered measurable when they are superficial (e.g., skin nodules and palpable lymph nodes) and ≥ 10 mm diameter as assessed using calipers (e.g., skin nodules). In the case of skin lesions, documentation by color photography, including a ruler to estimate the size of the lesion, is recommended.

12.2.3.2 **Chest x-ray:** Lesions on chest x-ray are acceptable as measurable lesions when they are clearly defined and surrounded by aerated lung. However, CT is preferable.

12.2.3.3 **Conventional CT and MRI:** This guideline has defined measurability of lesions on CT scan based on the assumption that CT slice thickness is 5 mm or less. If CT scans have slice thickness greater than 5 mm, the minimum size for a measurable lesion should be twice the slice thickness. MRI is also acceptable in certain situations (e.g. for body scans). Ideally, the same type of scanner should be used and the image acquisition protocol should be followed as closely as possible to prior scans.

12.2.3.4 **PET-CT:** At present, the low dose or attenuation correction CT portion of a combined PET-CT is not always of optimal diagnostic CT quality for use with RECIST measurements. However, if the site can document that the CT performed as part of a PET-CT is of identical diagnostic quality to a diagnostic CT (with IV and oral contrast), then the CT portion of the PET-CT can be used for RECIST measurements and can be used interchangeably with conventional CT in accurately measuring cancer lesions over time. Note, however, that the PET portion of the CT introduces additional data which may bias an investigator if it is not routinely or serially performed.

12.2.3.5 **Tumor markers:** Tumor markers alone cannot be used to assess response. If markers are initially above the upper normal limit, they must normalize for a patient to be considered in complete clinical response.

12.2.3.6 **Cytology, Histology:** These techniques can be used to differentiate between partial responses (PR) and complete responses (CR) in rare cases (e.g., residual lesions in tumor types, such as germ cell tumors, where known residual benign tumors can remain).

Cytology should be obtained if an effusion appears or worsens during treatment when the measurable tumor has met criteria for response or stable disease.

12.2.3.7 **FDG-PET:** While FDG-PET response assessments need additional study, it is sometimes reasonable to incorporate the use of FDG-PET scanning to complement CT scanning in assessment of progression (particularly possible 'new' disease). New lesions on the basis of FDG-PET imaging can be identified according to the following algorithm:

- a. Negative FDG-PET at baseline, with a positive FDG-PET at follow-up is a sign of PD based on a new lesion.
- b. No FDG-PET at baseline and a positive FDG-PET at follow-up: If the positive FDG-PET at follow-up corresponds to a new site of disease confirmed by CT, this is PD. If the positive FDG-PET at follow-up is not confirmed as a new site of disease on CT, additional follow-up CT scans are needed to determine if there is truly progression occurring at that site (if so, the date of PD will be the date of the initial abnormal FDG-PET scan). If the positive FDG-PET at follow-up corresponds to a pre-existing site of disease on CT that is not progressing on the basis of the anatomic images, this is not PD.

NOTE: A 'positive' FDG-PET scan lesion means one that is FDG avid with an uptake greater than twice that of the surrounding tissue on the attenuation corrected image.

12.2.4 Response Criteria for Patients with Solid Tumor and Measurable Disease

12.2.4.1 **Evaluation of Target Lesions**

Complete Response (CR): Disappearance of all target and non-target lesions. Any pathological lymph nodes (whether

target or non-target) must have reduction in short axis to <10 mm. If immunocytology is available, no disease must be detected by that methodology. Normalization of urinary catecholamines or other tumor markers if elevated at study enrollment (for patients with neuroblastoma).

Partial Response (PR):

At least a 30% decrease in the sum of the diameters of target lesions, taking as reference the baseline sum diameters

Progressive Disease (PD):

At least a 20% increase in the sum of the diameters of target lesions, taking as reference the smallest sum on study (this includes the baseline sum if that is the smallest on study). In addition to the relative increase of 20%, the sum must also demonstrate an absolute increase of at least 5 mm. (Note: the appearance of one or more new lesions is also considered progressions). Note: in presence of SD or PR in target disease but unequivocal progression in non-target or non-measurable disease, the patient has PD if there is an overall level of substantial worsening in non-target disease such that the overall tumor burden has increased sufficiently to merit discontinuation of therapy

Stable Disease (SD):

Neither sufficient shrinkage to qualify for PR nor sufficient increase to qualify for PD, taking as reference the smallest sum diameters while on study

12.2.4.2 Evaluation of Non-Target Lesions

Complete Response (CR):

Disappearance of all non-target lesions and normalization of tumor marker level. All lymph nodes must be non-pathological in size (<10 mm short axis)

Note: If tumor markers are initially above the upper normal limit, they must normalize for a patient to be considered in complete clinical response.

Non-CR/Non-PD:

Persistence of one or more non-target lesion(s) and/or maintenance of tumor marker level above the normal limits

Progressive Disease (PD):

Appearance of one or more new lesions and/or *unequivocal progression* of existing non-target lesions. *Unequivocal progression* should not normally trump target lesion status. It must be representative of overall disease status change,

not a single lesion increase.

12.2.5 Overall Response Assessment

Table 2. For Patients with Measurable Disease (i.e., Target Disease)

Target Lesions	Non-Target Lesions	New Lesions	Overall Response	Best Overall Response when Confirmation is Required*
CR	CR	No	CR	≥ 28 days Confirmation
CR	Non-CR/Non-PD	No	PR	≥ 28 days Confirmation
CR	Not evaluated	No	PR	
PR	Non-CR/Non-PD/not evaluated	No	PR	
SD	Non-CR/Non-PD/not evaluated	No	SD	documented at least once ≥ 28 days from baseline
PD	Any	Yes or No	PD	no prior SD, PR or CR
Any	PD**	Yes or No	PD	
Any	Any	Yes	PD	

* See RECIST 1.1 manuscript for further details on what is evidence of a new lesion.
 ** In exceptional circumstances, unequivocal progression in non-target lesions may be accepted as disease progression.

Note: Patients with a global deterioration of health status requiring discontinuation of treatment without objective evidence of disease progression at that time should be reported as “*symptomatic deterioration*.” Every effort should be made to document the objective progression even after discontinuation of treatment.

Table 3. For Patients with Non-Measurable Disease (i.e., Non-Target Disease)

Non-Target Lesions	New Lesions	Overall Response
CR	No	CR
Non-CR/non-PD	No	Non-CR/non-PD*
Not all evaluated	No	not evaluated
Unequivocal PD	Yes or No	PD
Any	Yes	PD

* ‘Non-CR/non-PD’ is preferred over ‘stable disease’ for non-target disease since SD is increasingly used as an endpoint for assessment of efficacy in some trials so to assign this category when no lesions can be measured is not advised

Table 4. Overall Response for Patients with Neuroblastoma and Measurable Disease

CT/MRI	MIBG	Bone Scan	Bone Marrow	Catechol	Overall
PD	Any	Any	Any	Any	PD
Any	PD	Any	Any	Any	PD
Any	Any	PD	Any	Any	PD
Any	Any	Any	PD	Any	PD
SD	CR/PR/SD	Non-PD	Non-PD	Any	SD
PR	CR/PR	Non-PD	Non-PD	Any	PR
CR/PR	PR	Non-PD	Non-PD	Any	PR
CR	CR	Non-PD	Non-PD	Elevated	PR
CR	CR	CR	CR	Normal	CR

12.2.6 Overall Best Response Assessment

Each patient will be classified according to his “best response” for the purposes of analysis of treatment effect. Best response is determined as outlined in [Section 12.7](#) from a sequence of overall response assessments.

12.3 **Response Criteria for Patients with Solid Tumors and Evaluable Disease****12.3.1 Evaluable Disease**

The presence of at least one lesion, with no lesion that can be accurately measured in at least one dimension. Such lesions may be evaluable by nuclear medicine techniques, immunocytochemistry techniques, tumor markers or other reliable measures.

12.3.2 Complete Response

Disappearance of all evaluable disease.

12.3.3 Partial response

Partial responses cannot be determined in patients with evaluable disease.

12.3.4 Stable Disease (SD)

That which does not qualify as Complete Response (CR), Partial Response (PR), or Progressive Disease.

12.3.5 Progressive Disease

The appearance of one or more new lesions or evidence of laboratory, clinical, or radiographic progression.

12.3.6 Overall Best Response Assessment

Each patient will be classified according to his “best response” for the purposes of analysis of treatment effect. Best response is determined as outlined in [Section 12.7](#) from a sequence of overall response assessments.

12.4 **Response Criteria for Neuroblastoma Patients with MIBG Positive Lesions****12.4.1 MIBG Positive Lesions**

Patients who have a positive MIBG scan at the start of therapy will be evaluable for MIBG response. The use of ^{123}I for MIBG imaging is recommended for all scans. If the patient has only one MIBG positive lesion and that lesion was radiated, a biopsy must be done at least 28 days after radiation was completed and must show viable neuroblastoma.

12.4.2 The following criteria will be used to report MIBG response by the treating institution:

Complete response: Complete resolution of all MIBG positive lesions

Partial Response: Resolution of at least one MIBG positive lesion, with persistence of other MIBG positive lesions

Stable disease: No change in MIBG scan in number of positive lesions

Progressive disease: Development of new MIBG positive lesions

12.4.3 The response of MIBG lesions will be assessed on central review using the Curie scale¹⁴ as outlined below. Central review responses will be used to assess efficacy

[figure not shown]
for study endpoint. See [Section 8.2.1](#) for details on transferring images to the Imaging Research Center.

NOTE: This scoring should also be done by the treating institution for end of course response assessments.

The body is divided into 9 anatomic sectors for osteomedullary lesions, with a 10th general sector allocated for any extra-osseous lesion visible on MIBG scan. In each region, the lesions are scored as follows. The **absolute extension score** is graded as:

- 0 = no site per segment,
- 1 = 1 site per segment,
- 2 = more than one site per segment,
- 3 = massive involvement (>50% of the segment).

The **absolute score** is obtained by adding the score of all the segments. See diagram of sectors below:

The **relative score** is calculated by dividing the absolute score at each time point by the corresponding pre-treatment absolute score. The relative score of each patient is calculated at each response assessment compared to baseline and classified as below:

1. **Complete response:** all areas of uptake on MIBG scan completely resolved. If morphological evidence of tumor cells in bone marrow biopsy or aspiration is present at enrollment, no tumor cells can be detected by routine morphology on two subsequent bilateral bone marrow aspirates and biopsies done at least 21 days apart to be considered a **Complete Response**.
2. **Partial response:** Relative score ≤ 0.2 (lesions almost disappeared) to ≤ 0.5 (lesions strongly reduced).
3. **Stable disease:** Relative score > 0.5 (lesions weakly but significantly reduced) to 1.0 (lesions not reduced).
4. **Progressive disease:** New lesions on MIBG scan.

12.4.4 Overall Response Assessment

Table 5. Overall Response Evaluation for Neuroblastoma Patients and MIBG Positive Disease Only

If patients are enrolled without disease measurable by CT/MRI, any new or newly identified lesion by CT/MRI that occurs during therapy would be considered progressive disease.

MIBG	CT/MRI	Bone Scan	Bone Marrow	Catechol	Overall
PD	Any	Any	Any	Any	PD
Any	New Lesion	Any	Any	Any	PD
Any	Any	PD	Any	Any	PD
Any	Any	Any	PD	Any	PD
SD	No New Lesion	Non-PD	Non-PD	Any	SD
PR	No New Lesion	Non-PD	Non-PD	Any	PR
CR	No New Lesion	Non-PD	Non-PD	Elevated	PR
CR	No New Lesion	CR	CR	Normal	CR

12.4.5 Overall Best Response Assessment

Each patient will be classified according to his “best response” for the purposes of analysis of treatment effect. Best response is determined from the sequence of the overall response assessments as described in Table 6 in [Section 12.7](#).

12.5 Response Criteria for Neuroblastoma Patients with Bone Marrow Involvement

12.5.1 Bone Marrow Involvement

Bone marrow obtained within 28 days prior to study enrollment with tumor cells seen on routine morphology (not by immunohistochemical staining only) of bilateral aspirate or biopsy on one bone marrow sample.

Bone Marrow responses are determined by H&E Staining of bilateral bone marrow biopsies and aspirates.

Complete Response: No tumor cells detectable by routine morphology on 2 consecutive bilateral bone marrow aspirates and biopsies performed at least 21 days apart. Normalization of urinary catecholamines or other tumor markers if elevated at study enrollment.

Progressive Disease: In patients who enroll with neuroblastoma in bone marrow by morphology have progressive disease if there is a doubling in the amount of tumor in the marrow AND a minimum of 25% tumor in bone marrow by morphology. (For example, a patient entering with 5% tumor in marrow by morphology must increase to $\geq 25\%$ tumor to have progressive disease; a patient entering with 30% tumor must increase to $> 60\%$).

In patients who enroll without evidence of neuroblastoma in bone marrow will be defined as progressive disease if tumor is detected in 2 consecutive bone marrow biopsies

or aspirations done at least 21 days apart.

Stable Disease: Persistence of tumor in bone marrow that does not meet the criteria for either complete response or progressive disease.

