4.1.7 Organ Function Requirements

4.1.7.1 Adequate Bone Marrow Function defined as:

- a. For patients with solid tumors without known bone marrow involvement:
 - Peripheral absolute neutrophil count (ANC) $\geq 1000/\text{mm}^3$
 - Platelet count $\geq 100,000/\text{mm}^3$ (transfusion independent, defined as not receiving platelet transfusions for at least 7 days prior to enrollment).
 - Hemoglobin $\geq 8 \text{ g/dL}$
- b. Patients with known bone marrow metastatic disease will be eligible for study provided they meet the blood counts in [Section 4.1.7.1.a](#) (may receive transfusions provided they are not known to be refractory to red cell or platelet transfusions). These patients will not be evaluable for hematologic toxicity. At least 5 of every cohort of 6 patients on Part A1 must be evaluable for hematologic toxicity for the dose-escalation part of the study. If dose-limiting hematologic toxicity is observed, all subsequent patients enrolled must be evaluable for hematologic toxicity.

4.1.7.2 Adequate Renal Function defined as:

- Creatinine clearance or radioisotope GFR $\geq 70 \text{ mL/min}/1.73 \text{ m}^2$ or
- A serum creatinine based on age/gender as follows:

Age	Maximum Serum Creatinine (mg/dL)	
	Male	Female
6 months to < 1 year	0.5	0.5
1 to < 2 years	0.6	0.6
2 to < 6 years	0.8	0.8
6 to < 10 years	1	1
10 to < 13 years	1.2	1.2
13 to < 16 years	1.5	1.4
≥ 16 years	1.7	1.4

The threshold creatinine values in this Table were derived from the Schwartz formula for estimating GFR (Schwartz et al. J. Peds, 106:522, 1985) utilizing child length and stature data published by the CDC.

4.1.7.3 Adequate Liver Function defined as:

- Bilirubin (sum of conjugated + unconjugated) \leq upper limit of normal (ULN) for age
- SGPT (ALT) \leq 135 U/L. For the purpose of this study, the ULN for SGPT is 45 U/L.
- SGOT (AST) \leq 150 U/L. For the purpose of this study, the ULN for SGOT is 50 U/L.
- Serum albumin \geq 2.7 g/dL

4.1.7.4 Adequate Cardiac Function defined as:

- Shortening fraction of \geq 27% by echocardiogram, or
- Ejection fraction of \geq 50% by gated radionuclide study.
- No supraventricular arrhythmia on EKG
- Prolonged rate corrected QT (QTc) interval $<$ 500 msec

4.1.7.5 Adequate Pulmonary Function defined as:

- Pulse oximetry $>$ 94% on room air if there is clinical indication for determination (e.g. dyspnea at rest).

4.1.7.6 Adequate Neurologic Function defined as:

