10.0 CRITERIA FOR REMOVAL FROM PROTOCOL THERAPY AND OFF STUDY CRITERIA

10.1 Criteria for Removal from Protocol Therapy

- a) Clinical (including physical examination or serum tumor markers) or radiographic evidence of progressive disease (See [Section 12.0](#))
- b) Adverse Events requiring removal from protocol therapy (See [Section 6.0](#))
- c) Refusal of protocol therapy by patient/parent/guardian
- d) Non-compliance that in the opinion of the investigator does not allow for ongoing participation.
- e) Completion of 17 cycles of therapy.
- f) Physician determines it is not in the patient's best interest.
- g) Repeated eligibility laboratory studies (CBC with differential, bilirubin, ALT (SGPT) or serum creatinine) are outside the parameters required for eligibility prior to the start of pevonedistat (See [Section 8.1](#)).
- h) Study is terminated by Sponsor.
- i) Pregnancy

Patients who are removed from protocol therapy during Cycle 1 should continue to have the required observations in [Section 8.1](#) until the originally planned end of the cycle or until all adverse events have resolved per [Section 13.4.4](#), whichever happens LATER. The only exception is with documentation of the patient's withdrawal of consent. Patients who are removed from protocol therapy in subsequent cycles should have the necessary observations to ensure adequate clinical care.

Patients who are off protocol therapy are to be followed until they meet the criteria for Off Study (see below). Ongoing adverse events, or adverse events that emerge after the patient is removed from protocol therapy, but within 30 days of the last dose of investigational agent, must be followed and reported via RAVE and CTEP-AERS (if applicable). Follow-up data will be required unless consent is withdrawn.

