12.7 Best Response

12.7.1 Evaluation of Best Overall Response

The best overall response is the best response recorded from the start of the treatment until disease progression/recurrence (taking as reference for progressive disease the smallest measurements recorded since the treatment started). The patient's best response assignment will depend on the achievement of both measurement and confirmation criteria.

Table 6. Sequences of overall response assessments with corresponding best response.

1 st Assessment	2 nd Assessment	Best Response
Progression		Progressive disease
Stable, PR, CR	Progression	Progressive disease
Stable	Stable	Stable
Stable	PR, CR	Stable
Stable	Not done	Not RECIST classifiable
PR	PR	PR
PR	CR	PR
PR, CR	Not done	Not RECIST classifiable
CR	CR	CR

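### Section 12.5.1 cannot register marrow progression, measured from entry, in neuroblastoma patients who enter with more than 50% marrow tumor; their worsening marrow counts as stable

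*Combined protocol and SAP*

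**What the plan says.** Section 12.5.1 of the protocol sets two conditions for marrow progression in patients who enroll with morphologic marrow disease, and both must hold: "there is a doubling in the amount of tumor in the marrow AND a minimum of 25% tumor in bone marrow by morphology". Two examples follow. In one, "a patient entering with 5% tumor in marrow by morphology must increase to" at least 25%. In the other, "a patient entering with 30% tumor must increase to" more than 60%.

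A separate rule covers patients with a negative marrow at entry: "In patients who enroll without evidence of neuroblastoma in bone marrow will be defined as progressive disease if tumor is detected" on two consecutive samples. Stable disease is the residual category: "Persistence of tumor in bone marrow that does not meet the criteria for either complete response or progressive disease".

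Tables 4 and 5 (Sections 12.2.5 and 12.4.4) combine the marrow result with CT/MRI, MIBG, bone scan and catecholamines. A marrow classed as Non-PD is compatible with an overall SD and with an overall PR.

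On who may enter, Section 4.1.7.1.b says: "Patients with known bone marrow metastatic disease will be eligible for study provided they meet the blood counts in" Section 4.1.7.1.a. It sets no upper limit on the marrow tumor percentage.

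For best response, Section 12.5.2 refers to Section 12.7. There, Section 12.7.1 uses a different reference: "taking as reference for progressive disease the smallest measurements recorded since the treatment started".

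**The concern.** A percentage cannot exceed 100, so a rule that requires doubling stops working once the starting value passes one half. Section 12.5.1 offers no alternative for that range, such as an absolute rise or a statement that marrow progression cannot be assessed. Because stable disease is defined as whatever is neither CR nor PD, the failure is silent. A marrow that clearly worsens is recorded as stable, not as unassessable.

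The response summary could therefore report stable disease, or a PR driven by imaging, in a patient whose marrow was filling with tumor. Duration of stable disease (Section 12.7.2) runs until progression criteria are met, so it could be lengthened too. Section 8.1 (footnote 8) repeats the marrow at every disease evaluation in patients who were positive at baseline. For this group, on the entry reference, those samples cannot register progression.

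**Working it through.** **Inputs.** All come from Section 12.5.1: a doubling; a 25% minimum; percentage by morphology as the scale and the entry value as the reference, both taken from the two examples.

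**Formula.** For entry percentage b, the progression threshold is T(b) = max(25, 2b). Progression is attainable only if T(b) is no more than 100.

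**The plan's own figures.** T(5) = max(25, 10) = 25 and T(30) = max(25, 60) = 60. Both examples are reproduced. The first is stated as at least and the second as more than.

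**Higher entry values.** The largest possible fold increase is 100/b.

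| Entry b (%) | T(b) (%) | Largest fold increase | Marrow PD attainable? |
|---|---|---|---|
| 40 | 80 | 2.50 | Yes |
| 49 | 98 | 2.04 | Yes |
| 50 | 100 | 2.00 | Only at 100% under at least; never under more than |
| 51 | 102 | 1.96 | No |
| 60 | 120 | 1.67 | No |
| 75 | 150 | 1.33 | No |
| 90 | 180 | 1.11 | No |

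**What this means for a patient.** A rise from 55% to 95% is 40 points and a factor of 95/55 = 1.73. T(55) = 110, so the marrow is stable. A rise from 12% to 25% is 13 points; T(12) = max(25, 24) = 25, so the marrow is progressive.

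**If the reference is the smallest value since treatment started (Section 12.7.1).** Put the smallest value n in place of b, for a patient entering at 60%:

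- n = 30: T = 60, attainable.
- n = 40: T = 80, attainable.
- n = 50: T = 100, attainable only at 100% under at least.
- n = 55: T = 110, not attainable.

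On either reference, progression stays out of reach if the marrow never falls to 50% or below.

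**How many patients.** The documents give no count. Section 4.1.7.1.b makes patients with known marrow metastases inevaluable for hematologic toxicity and requires at least 5 of every 6 in a Part A1 escalation cohort to be evaluable. That leaves at most 6 − 5 = 1 marrow-involved patient, of any tumor type, per cohort of six. Over four dose levels of six it is 4 × 1 = 4. After a dose-limiting hematologic toxicity no more may enter. The limit does not expressly cover Part A2 or the PK expansion.

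**The case against.** A reader might infer that marrow progression in these patients is always scored as stable, that every one of them is misclassified, and that they stay on treatment as a result. The documents do not support that reading, for five reasons.

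- **Reference value.** Under Section 12.7.1 the reference is the smallest measurement. If that applies to marrow, a patient who falls from 60% to 30% can later progress.
- **Other routes to progression.** PD on CT/MRI, MIBG or bone scan gives overall PD whatever the marrow shows. For patients without measurable disease, Section 12.3.5 admits laboratory or clinical evidence of progression, which arguably includes a marrow result.
- **Treatment does not rest on this rule alone.** Section 5.3 does ask for at least stable disease before another cycle. But Section 10.1 removes patients for "Clinical (including physical examination or serum tumor markers) or radiographic evidence of progressive disease" and also on physician judgment, and footnote 5 of Section 8.1 lets the investigator determine progression on clinical or laboratory evidence.
- **Misclassification is not certain.** Whether a given rise at high involvement is true progression is what the criterion is meant to decide.
- **Low stakes.** Antitumor activity is a secondary, preliminary aim (Section 1.2.1) and response is descriptive (Section 11.5). Responder status needs CR or PR confirmed by central review (Section 12.2.1.1), and no decision rule uses a stable-disease rate.

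All of this stands, and it narrows the point considerably. It does not remove it. None of these provisions makes the threshold in Section 12.5.1 attainable on the reference its own examples use. Section 8.2.1 describes central review of images, so it would not re-score a marrow. The other routes also leave one patient with two possible answers, depending on which section is applied.

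**Conclusion.** The rule is wrong as written, but the effect is narrow. On the entry reference, marrow progression is unattainable for every entry value above 50%, and at exactly 50% under the strict inequality of the 30% example. Worsening marrow then defaults to stable and enters Tables 4 and 5 as Non-PD.

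The consequence falls on neuroblastoma patients who enter above 50% and whose marrow is the only progressing site. It affects their descriptive response category and duration of stable disease. The MTD, DLT and PK results are untouched. In the Part A1 escalation cohorts the number is small, and the documents do not say whether any such patient has enrolled.

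The conclusion rests on two readings. First, the amount of tumor means the percentage of marrow by morphology, as both examples imply. Second, the reference is the entry value. If the smallest value is used instead, the gap shrinks to patients whose marrow never falls to 50% or below; a smallest value of exactly 50% also fails under the strict inequality.

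**What to change.** 1. In Section 12.5.1, for the response analysis, do not count persisting marrow tumor as Stable or Non-PD when the doubling threshold exceeds 100%. Record it as not evaluable for progression. State also how exactly 50% is handled, since the two examples use different inequalities. Marrow CR remains assessable as now.
2. Add the matching marrow entry to Tables 4 and 5 and state the overall category it leads to. At present their SD rows and all their PR rows require a Non-PD marrow.
3. Report these patients separately, with entry and follow-up marrow percentages listed.
4. Reconcile the entry reference in Section 12.5.1 with the smallest-measurement reference in Section 12.7.1, and say how both relate to laboratory or clinical progression in Section 12.3.5.

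PD also governs removal from therapy and the start of further cycles. Any numeric progression cut-off for high entry values is therefore for the sponsor to decide, and none is proposed here.

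The cost is a text edit to Section 12.5.1 and two tables, plus the reconciliation. It needs no new procedures or patients. The downside is that a few patients move from stable disease to not evaluable, including some whose marrow was truly stable or falling; the separate listing keeps that visible.
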